[name], Co-Investigator, [name], [contact], [contact]

[name], Co-Investigator, [name], [contact], [contact]

[name], Co-investigator, [name], [contact], [contact]

[name], Co-investigator, [name], [contact]

[name], Dental Research Project Manager , GO Health Clinic, [name], [contact], [contact]

[name], Study Coordinator, [name], [contact], [contact]

[name], Research Assistant, [name], [contact], [contact]

[name], Research Assistant, GO Health Clinic, [name], [contact], [contact]

PARTICIPATING STUDY SITES

Study Site: UNC Adams School of Dentistry
GO Health Clinic, [name]
[name]
[name]
[contact] (P), [contact] (F)

PRÉCIS

Study Title

Antiviral Efficacy and Acceptability of Therapeutic Antiseptic Colgate Mouth Rinses for Inactivation of COVID SARS-2 Virus

Objectives

The primary objective is to quantify the impact of Colgate antiseptic mouthwashes on salivary infectivity in SARS-CoV-2+ patients. The secondary objectives are to quantitatively determine inflammatory cytokine and chemokine levels (pg/mL) in SARS-CoV-2+ patient blood and saliva and to evaluate the incidence of periodontal disease among study participants.

Design and Outcomes

Randomized, double-blind prospective trial to test the efficacy and acceptability of therapeutic, antiseptic mouth rinses to inactivate SARS-CoV-2 virus in saliva of SARS-CoV-2+ patients 18-65 years of age. All mouthrinses are commercially available Colgate products and will be used according to on-label instructions. Patients will be randomized to a mouthrinse and will be asked to give a saliva sample immediately before and after a 30-60 second mouthwash. Saliva samples will be collected from patients at 15-minute intervals thereafter up to one hour (15, 30, 45 and 60 min). The samples will be stored and used for RT-PCR detection of SARS-CoV-2 virus and viral infectivity assays, along with quantitative cytokine and chemokine concentration (pg/mL, Luminex). Patients will also complete a short survey on the taste and experience of using the mouthwash. Peripheral blood will be collected at the end of salivary collection. Participants, except controls, will be provided materials and oral hygiene instruction related to daily use of oral hygiene products provided by the study. In the seven-day period between study visits, participants will be directed to brush with Colgate toothpaste (at least twice per day) and rinse with the Colgate mouthrinse (according to on-label procedures). Controls are not given Colgate products and will be asked to carry out their typical oral hygiene regimen with the products they typically use. All participants will be asked to keep a daily diary of oral hygiene performance, product usage, COVID-19 symptoms and exposures. Daily diary data confirms compliance with oral hygiene protocol, and is needed for data inclusion and analysis, as it relates to secondary and tertiary outcomes for visit 2. Participants will be scheduled to return to the GoHealth Clinical Research Unit at one week after the baseline assessment, during which additional salivary (1 time point, 2 mL of saliva over 5 min, no rinse will occur) and blood samples will be collected. At the conclusion of sample collection, the participant will undergo a periodontal exam. Study participation concludes following the periodontal exam at the end of the second on site study visit. Patients with any periodontitis or gingivitis diagnosis will be informed of their diagnosis and will be referred to an oral healthcare provider for further treatment. Patients' final periodontal status will be a tertiary outcome of the periodontal exam and will be reported as the percentage of participants categorized into each diagnostic group; patients with a periodontal diagnosis will be informed of the findings and will be referred to an oral healthcare provider for further treatment. Participants who provide salivary and blood samples and follow study protocols will receive a \$30 gift card as compensation at the end of visit 1 and \$50 at the end of visit 2. This study involves two 90-minute visits.

Interventions and Duration

Subjects will have a brief oral exam and will be asked to rinse with an unlabeled/blinded antiviral mouth rinse for 30-60 sec and provide 2 mL of saliva prior to the rinse and 2 mL of saliva

immediately post-rinse, 15 min post-rinse, 30 min post-rinse, 45 min post-rinse, and 60 min post-rinse. Subjects will also be asked to complete a short survey about the rinsing experience. A blood sample will be taken. Subjects will be onsite for a 90 min initial visit appointment. Patients will be sent home with Colgate toothpaste and mouthrinse for a daily oral health regimen, where participants will brush and rinse twice daily and maintain a take-home diary on their oral care regimen and COVID-19 symptoms. Patients will return for a second visit one week later for a salivary sample, blood draw and periodontal exam.

Sample Size and Population

We will enroll 30 outpatient SARS-CoV-2+ subjects per mouth rinse, (to achieve a total of 25 subjects with full data sets per mouth rinse,) with 5 mouth rinses, requiring us to enroll 125 SARS-CoV-2+ patients. Patients will be randomized to their mouthrinse. These patients will have already had a confirmed SARS-CoV-2+ test prior to enrollment. There will be no stratification to our randomization. In addition to having a SARS-CoV-2+ test, patients will need to be at least 18 y.o.a. and at most 65 y.o.a. and in fair oral health without any known allergies or reactions to commercial dental products or mouthrinses. Patients who are pregnant, nursing/lactating, have a cognitive or developmental disability, have kidney dysfunction, have an active oral herpes flare up, have any oral viral infection and/or flare up, have significant mucosal tears, growths or damage to their mouth, have uncontrolled severe periodontal disease with bleeding gums, or those with severe xerostomia will be excluded from the study. There are no exclusion criteria based on gender or race.

Table of Abbreviations and Definition of Terms

Abbreviation / Term	Definition	Additional details or range of value
baseline	Refers to the blood and saliva sample collection time point prior to mouth rinse use at study visit 1.	
BOP	Bleeding on probing- sites where the gingiva/gum bleeds after probing	0 not bleeding; 1 bleeding
CDART	Carolina Data Acquisition and Reporting Tool	0mm to 20mm, recession plus probing depth
CAL	Clinical attachment level	Probing depth plus recession (mm)
Co-I	Co-investigator	
CT	Cycle threshold	refers to the number of cycles needed to amplify viral RNA to reach a detectable level
Cytokine / chemokines assessed in this study	Interleukin-6 (IL-6), Interleukin-10 (IL-10), Interleukin-8 (IL-8), C-X-C Motif Chemokine Ligand 10 (CXCL-10)	
EDTA	Ethylenediaminetetraacetic acid	

FBS	Fetal bovine serum	
GI	Modified Gingival index	0-3
hr	hours	
infectivity	Reduction factor in infectivity	
MEM	Minimum essential media	
mL	milliliters	
mRNA	Messenger ribonucleic acid	
OD	Optical density	Measured in nm on a spectrophotometer retrofitted with a plate reader
PBS	Phosphate buffered saline	
PFU	Plaque forming units	
pg	picogram	
PHI	Protected health information	
PI	Principle investigator or modified Plaque Index (depends on context)	0-3
PD, PPD	Periodontal Probing depth (PPD, PD); pocket depth- Refers to pocket depth (measured in mm) upon periodontal probing	0 to 15mm; measured with a periodontal probe
RDC	Respiratory Diagnostic Center	
RF	Reduction factor RF values [= log10 (loadpre / loadpost)]	RF will be calculated as the difference in the quotient of the infection titre before ('control titration') and after the mouthrinse ('remaining virus'). The log10 titre and its (double) standard deviation (SD) will be calculated as well as the variance of the RF.
RNA	Ribonucleic acid	
RQ	Relative quantification for RQ the $-\Delta\Delta Ct$ values [=log2 (2 $^{-\Delta\Delta Ct}$)]	RQ will be calculated to determine viral transcript changes across the time course for each individual participant. RQ is calculated using the 2(-delta delta Ct) method.
RT-PCR	Reverse transcription - polymerase chain reaction	
SD	Standard deviation	

sec	seconds	
y.o.a.	Years of age	
°C	Degrees celsius	
µL	microliters	

1.1 Primary Objective:

The primary objective of this study is to determine the efficacy of antiseptic mouthwashes on reducing SARS-CoV-2 cellular infectivity in COVID+ patient saliva. *We hypothesize that SARS-CoV-2+ patients will have a >20% reduction in SARS-CoV-2 viral infectivity following a 60 second oral rinse with an antiseptic mouthrinse and that this reduction will persist for at least 30 minutes.* This primary objective will focus on quantifying SARS-CoV-2 viral infectivity (Reduction Factor (RF) calculated from plaque forming units [PFU] / mL) and viral titer (Relative Quantification (RQ) ratio) using an *in vitro* infectivity assay and RT-PCR. This objective provides urgently needed data to guide healthcare workers on the proper use of specific commercially available mouthwashes capable of reducing SARS-CoV-2 viral infectivity and potentially limiting SARS-CoV-2+ transmission.

1.2 Secondary Objective:

The secondary objectives are to measure cytokine and chemokine levels (pg/mL) in samples taken from SARS-CoV-2+ patients and also to determine the frequency of periodontal disease among SARS-CoV-2+ patients. *We hypothesize that SARS-CoV-2+ patients using Colgate oral health products will have lower inflammatory marker levels than controls. Furthermore, we hypothesize that SARS-CoV-2+ patients will have a greater incidence of periodontal disease than the general population.*

1.3 Tertiary Objective (*Exploratory*):

The tertiary objective of this study is to use post-rinse surveys to evaluate patient perceptions of the mouthrinse and feedback on their willingness to use the product (units: percentage of respondents). Additionally, a periodontal exam will be performed to assess periodontal health. Patients' final periodontal status will be the tertiary outcome of the periodontal exam and will be reported as the percentage of participants categorized into each diagnosis. This tertiary outcome is exploratory.

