5. STUDY INTERVENTIONS

5.1 Interventions, Administration, and Duration

Patients who meet all inclusion criteria without any exclusions will be asked to give a baseline salivary sample of 2 mL over 5 min. The patient will then be asked to rinse with an unlabeled/blinded antiseptic mouth rinse for 60 sec. Once the participant expectorates the mouth rinse, a time 0, 2 mL salivary sample will be collected over 5 min. During the 10 min recuperation period post rinse, the participant will answer survey questions about their demographics and regarding the taste, color, flavor and acceptability of using the mouth rinse as part of routine dental and medical visits. At 15 min post-rinse, the patient will be asked to provide an additional 2 mL saliva sample over the course of 5 min, followed by another 10 min break. This sequence repeats for

the 30, 45 and 60-min time points. At 60 min, the patient will give a final 2 mL salivary sample. Peripheral blood will be collected at the end of salivary collection (2 - 5 mL in EDTA-containing blood collection tubes).

Participants will be provided materials and oral hygiene instruction related to daily use of oral hygiene products provided by study sponsors. In the one week between study visits, participants will be directed to brush with Colgate toothpaste (at least twice per day) and rinse with the Colgate mouthrinse (2-3 times per day based on-label directions). Participants will be asked to keep a daily diary of oral hygiene performance, product usage, COVID symptoms and exposures. Study personnel will monitor daily diary adherence and will reach out to participants between visits 1 and 2 to ensure home oral hygiene protocol adherence by phone or email. Participants will be given a \$30 gift card for their participation in visit 1.

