10.5.2 Secondary Outcomes

The secondary objectives are to measure inflammation-associated cytokine and chemokine concentration (pg/mL) in saliva and blood samples taken from SARS-CoV-2+ participants and also to determine the frequency of periodontal disease among participants. *We hypothesize that SARS-CoV-2+ participants using Colgate oral health products will have lower blood and salivary inflammation-associated cytokine and chemokine concentrations (pg/mL) than non-intervention controls. Furthermore, we hypothesize that SARS-CoV-2+ participants will have a greater incidence of periodontal disease than the general population.* Outcome assessments will be conducted weeks to months after the study visit, when statistical analyses are conducted.

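### At visit 2 the contrast with control tests Colgate products together with hygiene instruction and a brushing direction, so a marker difference cannot be credited to the products alone

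*Combined protocol and SAP*

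**What the plan says.** The home phase between visits 1 and 2 is set out by arm in only one place, the Précis under Design and Outcomes. There, "Participants, except controls, will be provided materials and oral hygiene instruction related to daily use of oral hygiene products provided by the study". For the week between visits, "participants will be directed to brush with Colgate toothpaste (at least twice per day) and rinse with the Colgate mouthrinse (according to on-label procedures"). For the comparator, "Controls are not given Colgate products and will be asked to carry out their typical oral hygiene regimen with the products they typically use". The daily diary is the one home task that this text assigns to everyone.

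The secondary hypothesis in 1.2, repeated in 10.2, is that "patients using Colgate oral health products will have lower inflammatory marker levels than controls". Section 10.5.2 puts it as "lower blood and salivary inflammation-associated cytokine and chemokine concentrations (pg/mL) than non-intervention controls".

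Section 5.1 adds that study personnel "will reach out to participants between visits 1 and 2 to ensure home oral hygiene protocol adherence by phone or email". It does not limit this to any arm.

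For analysis, 10.6 plans repeated measures regression for the immunological parameters, with Tukey adjustment across arms and false discovery rate control across markers. The Secondary Outcomes text in section 10 speaks only of descriptive comparison. The covariates named in section 10 (Primary Outcomes, the table in 10.5.3, and 10.6) are age, sex or gender, race and BMI.

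**The concern.** Under the Précis, a participant in a product arm differs from a control in four ways at once: a supplied toothpaste, a supplied rinse, instruction on using them, and a minimum brushing frequency. The hypothesis names only the first two. More frequent or more careful brushing for a week could itself lower salivary inflammatory markers, and that shift would run in the direction of the hypothesis. An inert product could then be reported as lowering inflammation.

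This is a separate matter from the conflict over whether controls receive Colgate products. If that conflict is settled by following the Précis to the letter, the problem described here remains.

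**Working it through.** **Step 1. What differs between the arms, taking the Précis as it stands.**

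| Home-phase element | Four product arms | Control |
|---|---|---|
| Colgate toothpaste | yes | no, own product |
| Assigned Colgate rinse | yes | no |
| Materials and product-use instruction | yes | no |
| Direction to brush at least twice a day | yes | no, usual routine |
| Daily diary | yes | yes |
| Phone or email contact (5.1) | not limited by arm | not limited by arm |

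**Step 2. Can design or analysis separate the elements?** Every product arm has all of the first four elements and the control arm has none. The design therefore has no contrast of product with instruction held fixed, or the reverse. The listed covariates do not include brushing frequency, so diary data are not used for this. Adjusting for brushing recorded after randomisation would in any case not restore a randomised comparison.

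**Step 3. Which comparisons are affected?** The product arms share toothpaste, general instruction and brushing direction and differ in the rinse, so contrasts among them are free of this problem. The visit 1 infectivity samples are taken before the home phase begins. Only the visit 2 contrast with control is affected.

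**Step 4. How much could it matter?** The plan gives no sample size or power for the markers, so there is no figure to reproduce. The inputs are:

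- five arms of 25 with complete data (section 3);
- two-sided 0.05 with Tukey adjustment (10.6);
- a true product effect of zero;
- an assumed shift c, in SD units, caused by instruction and brushing direction alone and equal in all four product arms. The documents give no value for c, so 0.2, 0.3 and 0.5 are shown.

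Formulas and values, for one marker at visit 2:

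- Error degrees of freedom: 5 × (25 − 1) = 120.
- 5% studentized range point for 5 means and 120 df: q = 3.917. Equivalent critical t: 3.917/√2 = 2.77.
- Standard error of a difference: √(2/25) = 0.283 SD. Smallest significant difference: 2.77 × 0.283 = 0.78 SD.
- Shift over standard error: 0.2/0.283 = 0.71; 0.3/0.283 = 1.06; 0.5/0.283 = 1.77.

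The chance that at least one of the four correlated contrasts with control crosses the limit in the lower direction was found by simulation (400,000 trials per row):

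| Assumed shift c | A given product arm significantly lower | At least one of four significantly lower |
|---|---|---|
| 0 | 0.3% | about 1% |
| 0.2 SD | 2% | about 7% |
| 0.3 SD | 5% | about 13% |
| 0.5 SD | 16% | about 38% |

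Hand check on the last row, single arm: P(Z > 2.77 − 1.77) = P(Z > 1.00) = 16%.

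False discovery rate control across markers could lower these chances further.

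**The case against.** The strongest reply is that 10.5.2 already calls the comparators non-intervention controls. The hypothesis can then be read as intervention against no intervention, and randomisation estimates that validly. This stands as far as it goes: the package contrast is unbiased for the package. It does not stand for the wording in 1.2 and 10.2, which refers to use of the products, nor for a conclusion drawn in those terms.

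A second reply is that the instruction concerns the supplied products and so is largely part of dispensing them. That is fair for the instruction. The minimum brushing frequency is different, because it could be given with any toothpaste.

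A third is that sections 2.2, 3 and 5.1 and the Précis (Interventions and Duration) describe home products, instruction or both without excepting controls. That conflict is real and must be reconciled. The point here is conditional on the Précis text under Design and Outcomes.

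Several stronger readings are tempting, and the documents do not support them:

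- **A separate instruction session, or closer follow-up of the product arms only.** No session is described. Section 5.1 restricts contact to no arm, and controls also keep the diary that is monitored.
- **Nothing at visit 2 can be attributed to a rinse.** Contrasts among the product arms do not carry this confounding.
- **A false-positive risk of 14%, 27% or 60%.** Those figures belong to an unadjusted t-test of 100 pooled product users against 25 controls. The plan contains no such pooled test.
- **A demonstrated bias.** Controls may already brush twice a day, and the documents give no estimate of what a week of instruction does to these markers.
- **A compromised periodontal endpoint.** Final periodontal status is to be reported as percentages, and 10.5.3 assigns the tertiary outcomes no hypothesis.

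**Conclusion.** The point holds in a limited form. If the Précis defines the control arm, a visit 2 marker difference from control estimates Colgate products with instruction and a brushing direction against usual routine. It cannot be credited to the products alone. The direction of any bias favours the hypothesis, and its size is unknown. On assumed shifts of 0.2, 0.3 or 0.5 SD and no product effect, the chance that at least one product arm appears significantly lower than control is about 7%, 13% or 38%, against about 1% with no shift. Those figures rest on five arms of 25, one marker, equal shifts in the four product arms, and the Tukey adjustment in 10.6. If only descriptive comparison is made, as the Secondary Outcomes text says, the rejection rates do not apply but the attribution problem does.

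This concerns a secondary outcome and leaves the primary outcome untouched. It is worth correcting because correction is cheap.

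**What to change.** When the Précis (Design and Outcomes) is reconciled with the Précis (Interventions and Duration) and sections 2.2, 3 and 5.1, state that one product-neutral hygiene instruction and brushing direction, whatever the sponsor chooses, applies identically in all five arms. State that the between-visit contact is also the same in every arm. Controls would use their own products, and product-specific directions would be given only with the products. Simply striking the exception for controls from the Précis sentence would not do: controls would then be instructed on products that they do not receive, and 5.1 contains no such exception to strike.

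If controls are to stay uninstructed, restate the secondary hypothesis in 1.2, 10.2 and 10.5.2, and the planned conclusion, as Colgate products with oral hygiene instruction and brushing direction versus usual routine.

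The first option costs protocol wording and a few minutes of instruction for about 30 enrolled controls. Instructed controls may improve, so the contrast may be smaller. The second costs wording only and leaves a narrower claim.
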